Aim 3: To conduct preliminary analyses exploring whether emerging adults who receive the intervention demonstrate improvement in key symptom domains. Specifically, 40 youth will be randomized to either the integrated treatment or standard care. Primary outcomes will include substance abuse and PTSD. Secondary outcomes will include criminal justice involvement, adaptive functioning, and other mental health symptoms.

The results of the study will have a **significant impact on public health** by informing treatments for co-occurring SUD/PTSD among justice-involved transition age youth, a group at the highest risk for these problems. Demonstrating the efficacy of an integrated treatment approach will provide a valuable clinical tool for community-based therapists to employ in the context of existing evidence-based treatments. Further, should compelling indications of efficacy be found and safety and acceptability be established, these aims will position the research to advance to an appropriately powered randomized controlled trial.

A. SIGNIFICANCE

Prevalence and consequences of substance use problems among emerging adults. Transition age youth (i.e., emerging adults, ages 18-25) represent the age group with the **highest rates of initiation of substance use, increases in substance use, and progression of substance use into substance use disorders** (Chassin, Flora, & King, 2004; Delucchi, Matzger, & Weisner, 2008; SAMHSA, 2009). Substance use plays a significant role in many serious problems during this developmental period, including suicide (SAMHSA, 2010), automobile accidents (Hingson, Heeren, Winter, & Wechsler, 2005), and other lethal events. Emerging adults with SUDs also have increased rates of risky sexual behavior, increasing their chances of contracting HIV and other STDs (King, Nguyen, Kosterman, Bailey, & Hawkins, 2012). Further, SUDs significantly impede successful negotiation of important developmental tasks of this transitional age, leading to increased rates of unemployment and job instability and decreased college attendance (Bray et al., 2000; Mangione et al., 1999). Finally, emerging adults with SUDs represent a greatly underserved population, with a high likelihood of “slipping through the cracks” as they transition from child to adult substance use service providers ([name], Green, & Hoffman, 2009). **Thus, this group has a very high potential to present significant short- and long-term costs for individuals, families, and society.**

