The Trauma Assessment for Adults (TAA; Gray, Elhai, Owen, & Monroe, 2009) will be used to screen for exposure to traumatic events, as the diagnosis of PTSD or subthreshold PTSD is contingent upon the experience of a qualifying traumatic event. In addition, the TAA assesses current involvement in violent relationships and will be used to assess the exclusion criteria "currently in a domestic violence relationship."

The National Stressful Events Survey PTSD Short Scale (NSESP-SS) (Miller et al., 2013), a validated self-report measure of DSM-V PTSD symptoms, will be used to screen for PTSD. THE NSESP-SS is a 20-item measure including subscales for intrusion, avoidance, negative cognitive/mood alterations, and hyperarousal/reactivity. The reference period will be "since the crime event occurred" at the screening/BL assessment and "past month" for each subsequent assessment. It is likely that emerging adults with both clinical and sub-clinical levels of PTSD will benefit from this treatment; therefore, emerging adults will meet study criteria if they: (a) report an index trauma; (b) meet criteria for 2 of the 4 DSM-V PTSD symptom cluster and (d) have significant functional impairment (i.e., the recommendation for determining subthreshold PTSD using DSM-V criteria; McLaughlin et al., 2015). This instrument will be used at each of the assessments as well as once per week during the participant's scheduled sessions.

The Addiction Severity Index (ASI) (McLellan et al., 1988) is a structured interview that assesses demographic information as well as areas affected by substance use disorders: alcohol use, drug use, medical status, legal status, psychiatric, employment, gambling, cigarette smoking, and social functioning. Adequate interrater and test-retest reliability, and concurrent and discriminant validity, have been established (McLellan et al., 1985; Zanis et al., 1994). An abbreviated version will be administered at follow-up.

Timeline Follow-back (TLFB; Sobell et al., 1980) uses calendar prompts to elicit specific information about the frequency and intensity of substance use over time intervals with good test-retest reliability and validity (Sobell & Sobell, 1992). It will assess days and quantity of alcohol use and days of cocaine, opioid, benzodiazepine, marijuana or other drug use 3 months before treatment, every session throughout treatment, and since the last interview at follow-up.

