Random Assignment occurs after the BL evaluation. A computerized urn randomization procedure (Stout et al., 1994) will balance patients on gender and submission of a positive sample for any illicit drug (i.e., cocaine, amphetamine, methamphetamine, opiate, benzodiazepine, or marijuana) at baseline, because positive samples at treatment initiation are related to poor outcomes (Preston et al., 1998; Silverman et al., 1998; Stitzer et al., 2007). Prior to randomizing participants, up to 10 pilot participants will complete a pilot study consent form and study procedures described for Group B below, through month 3 follow-up, for the purpose of monitoring staff on study procedures prior to the randomized trial.

Group A (Standard care [SC]; n=20) patients will receive SC at the substance use clinic where they are seeking treatment. This treatment approach typically consists of group therapy sessions, including daily planning, 12-Step treatment, relapse prevention, coping and life skills training, and AIDS education. Groups are led by recovering individuals, nurses, and masters level counselors. Very few individual sessions are provided at these clinics, and then only in cases of emergencies (e.g., suicidality). These clinics rarely conduct breathalyzers or urine testing for illicit drug use. Any such testing will occur as it normally would, and study procedures will not

impact standard care in any way. If the participant is not already enrolled in SC at a substance use clinic, they will be provided with referrals to clinics convenient to their home.

Study urine samples will be collected twice weekly. Patients will receive a \$5 payment (check or gift cards) for each of 20 urine/breath sample submissions during weeks 1-10. In addition, they will be asked to complete the NSSEP-SS and the CES-D to assess PTSD symptoms and depression weekly. If patients cease attending groups, they will still be encouraged to attend these brief meetings for sample monitoring. To maintain consistency with standard care in these clinics, results from toxicology screens will not be discussed with providers.

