Group B (SC + PE/CM Treatment; n=20) patients will receive the same SC groups as Group A. If they are currently enrolled in substance use treatment, they will continue with that treatment. If not, they will be provided with referrals for substance use treatment in the community. In addition, they will participate in an integrated Contingency Management (CM) and Prolonged Exposure (PE) treatment protocol described subsequently. Either the PI ([name]) or [name], will serve as the study therapist for participants randomized to group B. For cases where [name] serves as the therapist, [name] will provide clinical supervision of study cases.

As in Group A, participants will undergo testing twice weekly with a breathalyzer and urine drug screen. In addition, during the first meeting of the week, participants will engage in both CM and PE components of treatment (described below). During the second meeting of the week, participants will engage in CM and a brief check-in on the components of PE that the participant is working on for homework that week but no new PE-related components will be introduced.

Contingency Management Component. Participants in Group B will participate in CM to target abstinence from substance use. In prize CM protocols, participants earn opportunities to draw cards from a prize bowl. The cards differ in prize value, ranging from \$0 to \$100 in value, and participants can earn increasing numbers of draws with consecutive performance. The variable reinforcement amount feature of prize CM distinguishes it from other reinforcement systems such as voucher CM. Participants will be allowed to draw from the prize bowl if their urine drug screen is negative for opiates, methadone, cocaine, amphetamines, methamphetamines, and marijuana (see additional information about marijuana use below) and their breath screen is negative for alcohol.

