Feasibility measures relevant to recruitment and dropout proportions will be examined with 95% confidence intervals used to estimate the proportion of emerging adults who agree to participate out of the number deemed eligible and to compare those who complete versus do not complete the intervention. Feasibility will be evaluated by examining therapist adherence using ratings of taped sessions as well as emerging adults' responses to qualitative interviews. Measures of safety will include repeat trauma exposure, suicidal ideation, and risky substance use behaviors. Patterns of safety indicators will be examined using frequency distributions and descriptive statistics. In addition, rates of these indicators will be compared across Group A and Group B to determine if there is any increased risk posed by the active treatment compared to treatment as usual. These data will be used to make any necessary protocol changes.

Aim 3: To conduct a preliminary analysis of the efficacy of the integrated protocol in improving symptoms among emerging adults.

Groups will be compared with respect to the primary outcome variables (substance use, PTSD symptoms) and secondary variables (delinquent behaviors, depression, adaptive functioning, HIV risk behaviors). An important issue preceding analyses is to identify baseline differences between groups despite random assignment. Differences between groups that may be related to outcome will be used as covariates or fixed factors, as appropriate. We will conduct intent-to-treat analyses, with all randomized patients and apply random regression models, also known as hierarchical linear models (HLM), to determine if patients improve differentially between groups over time (Raudenbush & Bryk, 2002). HLM is specifically designed for repeated measures designs with missing data, allowing for intra-subject serial correlation and unequal variance and covariance structures over time by incorporating available trend data for each individual with information on the group from which the subject is drawn. Maximum likelihood estimation enables analyses to be performed for the full trial without having to drop subjects with incomplete data, and both continuous and dichotomous variables can be analyzed. If data cannot be normalized, group by time effects will

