be assessed with HLM, coding patients as improved or not at each time point. The main analyses will focus on during treatment effects (baseline through follow-up) but long-term effects (baseline to 3-month post-treatment follow-up) will also be analyzed (see follow-up section).

The primary outcomes are substance use is longest duration of abstinence from illicit drug use and symptoms of PTSD (NSESP-SS), continuous variables that can be transformed if needed. The primary substance use outcome is longest duration of abstinence from substances (LDA), the main outcome variable in most CM trials and the variable most strongly associated with long-term abstinence (Higgins et al., 1994, 2000, 2003; Petry et al., 2005). Linear regression will evaluate group differences in LDA, with condition as the independent variable (along with any important covariates). If data cannot be normalized, nonparametric tests will be used. While LDA is the primary substance use outcome measure, it is affected by retention as missing samples break a string of abstinence (unless preceded and followed by negative samples, and an excused 'miss' is obtained due to documented illness, court appearances, etc. usually comprising <5% of missed samples). Proportion of negative samples, in contrast, is unaffected by missing samples. Thus, we will also analyze proportion of samples negative for substances as a secondary outcome using similar analyses.

Analyses will focus on the 10-week during treatment effects, but long-term effects will also be analyzed. These will involve logistic regressions to predict substance abstinence at the 3-month follow-up, with treatment group and any important baseline characteristics (e.g., baseline sample result) included as independent variables. HLM analyses for dichotomous measures will also be conducted to evaluate substance abstinence over time between treatments from baseline throughout the 3-month follow-up. Additional secondary drug use outcomes will investigate abstinence from all substances concurrently and from each of the other drugs independently. These analyses will parallel those outlined above.

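### The LDA regression names no baseline covariate, and the only stated selection rule is observed imbalance; prespecifying one pre-treatment TLFB covariate is a cheap gain in precision

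*Combined protocol and SAP*

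**What the plan says.** All references are to the combined protocol and SAP.

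- **Outcome.** Data Analysis Strategy, Aim 3: "The primary substance use outcome is longest duration of abstinence from substances (LDA"). It is described in terms of samples: "it is affected by retention as missing samples break a string of abstinence" unless the miss is excused and has negative samples on both sides.
- **Model.** Same section: "Linear regression will evaluate group differences in LDA, with condition as the independent variable (along with any important covariates"). Which covariates count as important is not defined. Proportion of negative samples, a secondary outcome, gets similar analyses. If LDA cannot be normalised, nonparametric tests replace the regression, and no covariate is mentioned for them.
- **Selection rule.** Earlier in Aim 3 the plan says that baseline group differences are to be identified before analysis, and then: "Differences between groups that may be related to outcome will be used as covariates or fixed factors, as appropriate".
- **Available baseline data.** Assessments, Timeline Follow-back: the calendar covers days and quantity of alcohol use and days of use of other drug classes, including "marijuana or other drug use 3 months before treatment, every session throughout treatment, and since the last interview at follow-up". The assessment schedule lists it at baseline for every participant.
- **Size.** Specific Aims, Aim 3: "40 youth will be randomized to either the integrated treatment or standard care". The arms are "Group A (Standard care [SC]; n=20) patients" and "Group B (SC + PE/CM Treatment; n=20) patients".

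**The concern.** A baseline covariate that predicts the outcome reduces residual variance whether or not the arms differ on it. A rule driven by imbalance admits it only in the minority of trials where chance separates the arms, and so gives up most of the available precision. It also leaves the covariate set of a primary analysis open until group differences have been seen.

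The plan itself treats pre-treatment use as prognostic. Under Random Assignment it balances the urn on a positive baseline sample because such samples go with poor outcomes. That factor is one positive/negative result for illicit drugs and leaves out alcohol. The TLFB calendar records about 3 months of use, alcohol included, and neither the urn nor the LDA model uses it.

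At stake is the precision of a primary estimate from 40 people. Under Overview of Design, the trial's data are to support an application for a powered RCT. Under Contingency Plan, they also inform whether the intervention needs refining.

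**Working it through.** The plan gives no power, alpha, effect size or SD for LDA, so there is no figure of its own to reproduce.

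**Inputs from the documents.** n = 20 per arm; LDA analysed as a continuous outcome by linear regression on condition.

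**Assumptions.** Two-sided alpha 0.05; standardised effect d = 0.8 (0.5 as a check); correlation rho between baseline TLFB use and LDA from 0 to 0.7.

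**Step 1: unadjusted power.** Noncentrality = d × √(n/2) = 0.8 × √10 = 2.530, with 38 df and critical t = 2.024. Power is 69.3%.

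**Step 2: adjusted power.** The residual SD is multiplied by √(1 − rho²) and one df is lost (37 df, critical t = 2.026). Noncentrality = 2.530 / √(1 − rho²). Allowing for chance imbalance in the covariate divides this further by √(1 + 1/(2n − 4)) = √(1 + 1/36) = 1.014.

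| rho | Noncentrality before imbalance factor | Power, factor ignored | Power, factor included | Change from 69.3% (points) |
|---|---|---|---|---|
| 0 | 2.530 | 69.3% | 68.1% | −1.2 to 0 |
| 0.2 | 2.530/0.980 = 2.582 | 71.0% | 69.9% | +0.6 to +1.7 |
| 0.3 | 2.530/0.954 = 2.652 | 73.3% | 72.2% | +2.9 to +4.0 |
| 0.5 | 2.530/0.866 = 2.921 | 81.2% | 80.1% | +10.8 to +11.9 |

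With d = 0.5 and the imbalance factor included, power goes from 33.8% unadjusted to 35.7% at rho = 0.3 and 41.9% at rho = 0.5.

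**Step 3: the same gain as sample size.** Equivalent unadjusted N = 40/(1 − rho²): 40/0.91 = 44 at rho = 0.3 and 40/0.75 = 53 at rho = 0.5.

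**Step 4: what an imbalance rule recovers.** The plan states no threshold, so a baseline difference with p < 0.05 is assumed as the trigger. Simulation of 100,000 trials per row, normal outcomes:

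| d | rho | Never adjusted | Adjusted only if imbalanced | Always adjusted |
|---|---|---|---|---|
| 0.8 | 0.3 | 69.4% | 69.5% | 72.2% |
| 0.8 | 0.5 | 69.4% | 70.0% | 80.3% |
| 0.5 | 0.5 | 33.9% | 33.7% | 42.1% |
| 0 (type I error) | 0.5 | 5.0% | 4.3% | 5.0% |

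At d = 0.8 and rho = 0.5, the triggered rule recovers 70.0 − 69.4 = 0.6 of the available 80.3 − 69.4 = 10.9 points. It is also slightly conservative under the null.

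**The case against.** **The plan does not forbid the adjustment.** A reader might infer that TLFB use can enter the LDA model only if the arms differ on it. The text does not go that far. It allows important covariates without defining them, and the one example it gives of an important baseline characteristic, for the follow-up logistic model, is the baseline sample result, which the urn already balances. So important need not mean imbalanced. This stands: adjustment is permitted but neither required nor prespecified.

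**TLFB is not a baseline value of LDA.** LDA as described runs on twice-weekly samples over 10 weeks and depends on attendance; TLFB is recalled use. Under Contingency Management Component, marijuana can be detected for up to 3 to 4 weeks in heavy users, so someone who stops at once may test positive for up to 4/10 = 40% of the window. The entry criterion on cocaine and non-prescribed methadone or opiates may also narrow the baseline range. All of this can weaken the correlation. This stands too, and it is why no single value of rho should be relied on.

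**There is no power target to miss.** Aim 3 is preliminary, and the powered trial comes later. A reader might infer that the pilot is underpowered because of this omission; with no stated power, alpha or effect size, the documents do not support that.

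What survives is that the stated selection rule is a poor one, the data for a better one are already collected, and the cost if the covariate proves uninformative is small.

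**Conclusion.** The point holds in a limited form. The covariate set for LDA is not prespecified, and the only stated rule depends on observed imbalance, so a prognostic but balanced measure of pre-treatment use can be left out.

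The documents do not show that a large amount of power is lost. The benefit ranges from negligible at a correlation of 0.2 to material at 0.5, and nothing in the plan says which applies. These figures also assume roughly normal residuals, a linear relation, complete data on 20 per arm and an effect of 0.8. Against that, the downside is one degree of freedom, or about 1 point of power if the covariate is not prognostic. Fixing the covariate in advance also removes an analyst's choice from a primary analysis, whatever the correlation turns out to be. This is a cheap improvement, not an error that undermines the pilot.

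**What to change.** In Data Analysis Strategy, Aim 3, beside the LDA regression:

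- Name one TLFB covariate: days of any substance use, alcohol or drugs, in the 3 months before treatment. Include it as a fixed covariate for LDA and for proportion of negative samples, whether or not the arms differ.
- Replace selection by observed differences for these models. List any other covariate in the same sentence (the urn factors, gender and baseline sample result, are the natural candidates) and keep the set small for 40 participants.
- State that if LDA cannot be normalised, a covariate-adjusted rank-based analysis, such as rank ANCOVA, will be used with the same covariate.
- Settle whether LDA covers all substances or illicit drugs only, since the section uses both descriptions. The covariate above matches the all-substances definition.

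The cost is two or three sentences and one degree of freedom for the TLFB covariate. No new data are needed.

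### If LDA cannot be normalised, the plan falls back on unnamed nonparametric tests, and no LDA analysis is committed to the two urn factors; adjusting for them would be a free improvement

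*Combined protocol and SAP*

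**What the plan says.** In the combined protocol and SAP, Data Analysis Strategy, Aim 3, LDA is the primary substance use outcome. The analysis reads: "Linear regression will evaluate group differences in LDA, with condition as the independent variable (along with any important covariates"). The primary outcomes are described as "continuous variables that can be transformed if needed", and the last step is "If data cannot be normalized, nonparametric tests will be used". No test is named, no criterion for failure to normalise is given, and nothing says whether covariates stay in.

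The Random Assignment section states that the urn "will balance patients on gender and submission of a positive sample for any illicit drug". The reason given for the second factor is "because positive samples at treatment initiation are related to poor outcomes".

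The opening of Aim 3 selects covariates from baseline differences seen between the groups. Baseline sample result is mentioned as a covariate only once, as an example, and that is for the 3-month logistic regression. The plan's other fallback (mixed models with patients coded as improved or not) concerns group-by-time effects. It does not fit LDA, which is one value per patient.

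**The concern.** LDA comes from 20 scheduled samples, so it is bounded. Unexcused missed samples break a run, and heavy marijuana users may test positive for several weeks after stopping. Both can pile values up at the low end, where no transformation will normalise them, so the fallback may well be needed.

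The covariates are mentioned only as part of the regression, and the fallback replaces the regression. A standard two-group rank test has no place for them. When arms are balanced on a prognostic factor, the treatment estimate varies less than an unadjusted test assumes. The test then rejects too rarely under the null and wastes information under the alternative. At stake are some power on one of the two primary outcomes and an adjusted effect estimate in LDA units. That estimate would be useful for planning the later powered trial.

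**Working it through.** **Inputs from the documents.** The sample size is 40: "Specifically, 40 youth will be randomized to either the integrated treatment or standard care", with 20 per group. Samples are taken twice weekly for ten weeks, so there are 20 and LDA runs from 0 to 10 weeks. Women are expected to be 40% of the sample. No alpha, power, effect size or SD is stated for LDA, so there is no figure of the plan's to reproduce.

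**Assumptions.** Two-sided 5% test; half the patients positive at baseline; the strength of the baseline result (R², its share of LDA variance) varied, because the documents do not give it.

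**Step 1: formula, perfect balance on the factor.** The true size of a nominal 5% unadjusted test is 2 × [1 − Φ(1.96/√(1 − R²))].

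- R² = 0.1: 1.96/√0.9 = 2.066, size 3.9%
- R² = 0.2: 1.96/√0.8 = 2.191, size 2.8%
- R² = 0.3: 1.96/√0.7 = 2.343, size 1.9%

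For power, take a standardised difference d = 0.9 and SE = √(2/20) = 0.316. The unadjusted power is Φ[(d − 1.96·SE)/(SE·√(1 − R²))] and the adjusted power is Φ[d/(SE·√(1 − R²)) − 1.96]. Unadjusted against adjusted, these give 82.5% v 85.1% (R² = 0.1), 83.9% v 88.9% (0.2) and 85.5% v 92.5% (0.3).

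**Step 2: simulation with the actual design features.** There were 6,000 trials per setting, with N = 40 and a two-factor urn (one starting ball per arm, one added per assignment, the more imbalanced urn decides). LDA was the longest negative run in 20 samples with random dropout. The baseline result affected LDA to varying degrees; gender did not. Monte Carlo error is about 0.3 points for size and 0.6 for power.

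| R² (approx.) | Size: Mann-Whitney | Size: rank-ANCOVA, both urn factors | Power: Mann-Whitney | Power: rank-ANCOVA | Power gap |
|---|---|---|---|---|---|
| 0.03 (no true effect of baseline result) | 5.1% | 5.4% | 60.1% | 59.7% | −0.4 |
| 0.12 | 3.8% | 4.9% | 63.7% | 67.6% | 3.9 |
| 0.27 | 2.4% | 5.0% | 48.8% | 66.4% | 17.6 |

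With 20:20 randomisation and no balancing, Mann-Whitney size was 4.2%, 5.1% and 5.0%, with no trend. The conservatism therefore comes from balancing without adjusting.

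**Step 3: a second, separately built urn simulation.** At R² of about 0.03, 0.12 and 0.28, Mann-Whitney against rank-ANCOVA gave size 5.0% v 4.9%, 4.2% v 5.2% and 3.1% v 5.6%. Power was 45% v 46%, 41% v 44% and 33% v 42%, so the gaps were 1, 3 and 9 points. A van Elteren test stratified by baseline result performed like rank-ANCOVA.

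**Step 4: the regression, on the Step 2 data.** In the same R² order, linear regression without the urn factors had size 5.0%, 4.3% and 3.0% and power 60.7%, 60.9% and 43.4%. With both factors, power was 59.4%, 62.9% and 55.0%. The planned regression is thus conservative in the same way if its covariate rule leaves these factors out.

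**Step 5: how often the fallback would be used.** The plan sets no trigger. With an assumed one (Shapiro-Wilk failing on raw, square-root and log data), simulated LDA failed in about 3 to 32% of datasets. As an order of magnitude, 17.6 × 0.32 = 5.6 points and 3.9 × 0.32 = 1.2 points averaged over all trials. This supposes that the gap is the same when the trigger fires, which was not tested.

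**The case against.** The plan never says that covariates are dropped. A reader might infer that it does, but this is a reading of silence. Rank-ANCOVA and the van Elteren test are themselves nonparametric, and the general covariate rule at the start of Aim 3 has no exception for the fallback. That objection stands, so the point rests on the ordinary reading of the sentence and on the absence of any commitment to the urn factors.

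A reader might also infer that the fallback is worse than the planned regression. The documents do not support that. The regression names no covariate, and its selection rule looks for observed imbalance, which the urn makes less likely for exactly these factors. In Step 4, Mann-Whitney was at least as powerful as unadjusted regression at R² of about 0.12 and 0.27, and at about 0.12 it matched fully adjusted regression (63.7% v 62.9%).

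A third tempting reading is that the loss is certain. It is not. The plan calls baseline result prognostic but gives no strength. By their titles in the reference list, the studies cited for that statement concern cocaine or stimulants, whereas entry here requires a cocaine-negative screen. A strong R² cannot simply be carried over.

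Finally, Aim 3 is a preliminary analysis with no power claim, and a conservative test does not create false positives. That limits the importance of the point but does not remove it, because the adjusted analysis uses data already collected and costs essentially no power when the factor is weak.

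**Conclusion.** The point holds in conditional form. The LDA fallback is unnamed and on its ordinary reading unadjusted, and neither it nor the regression commits to gender and baseline sample result. The size of the loss depends on R²: nothing at about 0.03; about 4 power points at about 0.12 (3 in the second simulation), with type I error of 3.8 to 4.2%; 9 to 18 points at about 0.27, with type I error of 2.4 to 3.1%. The direction follows from the plan's own statement that baseline result predicts outcome. The size rests on the assumed R², treatment effect, dropout and share of positive patients, and arises only if LDA fails to normalise. The power figures are averages over all simulated trials, not only those in which it would fail. This is a worthwhile improvement to a pilot's analysis, not an error that threatens its conclusions.

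**What to change.** Include gender and baseline sample result as covariates in the LDA linear regression, whatever baseline differences are observed. Replace the fallback sentence with:

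> *If LDA cannot be normalised, groups will be compared by rank-based ANCOVA adjusting for gender and baseline sample result (or a van Elteren test stratified by baseline sample result), and the adjusted difference in LDA will be reported with a permutation or bootstrap confidence interval.*

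Carrying over only the covariates of the linear model would not be enough, since that model currently commits to neither factor. One of the two rank methods should be chosen before data are seen, and the criterion for failure to normalise stated at the same time.

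The cost is two sentences in the analysis plan. Both factors are known before randomisation, so no data collection or patient burden is added.
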